- q. During HD, blood samples for MK-3866 will be collected from both the pre-dialyzer and post-dialyzer blood lines; thus 2 plasma samples per time point during HD will be taken. A blood sample (a pre-dialyzer and post-dialyzer) will also be obtained immediately before the HD is stopped, if this time point does not coincide with a time point that is already scheduled.
- r. Dialysate samples for determination of MK-3866 will be obtained pre-dialysis, post-dialysis (before the HD is stopped), and for 1 minute every half hour during HD.
- s. HD session will be initiated immediately following the 0.5-hour postdose blood draw.

Abbreviations: ConMed = Concomitant Medication, CRU = Clinical Research Unit, FU = Follow-Up, FSH = Follicle Stimulating Hormone, HIV = Human Immunodeficiency Virus, IV = Intravenous, HD = Hemodialysis P = Predose, RI = Renal Impairment, S = Screening, UA = Urinalysis

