#### **10.1.5 Hemodialysis (ESRD Subjects Only)**

ESRD subjects on HD will receive HD as per their regular schedule and blood and dialysate sampling be collected as outlined in the Study Events Flow Chart ([Section 6](#)).

Dosing in Period 1 will occur immediately following completion of a normally scheduled HD session. For subjects following a Monday, Wednesday, Friday HD schedule, MK-3866 will be administered immediately following their Friday HD session. For subjects following a Tuesday, Thursday, Saturday HD schedule, MK-3866 will be administered immediately following their Saturday HD session. The 72-hour HD (either Monday or Tuesday) should initiate immediately following the 72-hour blood draw. If HD must be initiated prior to 72 hours postdose, a sample for MK-3866 analysis will be collected prior to HD, and the time recorded.

Dosing in Period 2 will occur approximately 30 minutes prior to the normally scheduled HD session. For subjects following a Monday, Wednesday, Friday HD schedule, MK-3866 will be administered prior to their Friday HD session. For subjects following a Tuesday, Thursday, Saturday HD schedule, MK-3866 will be administered prior to their Saturday HD

session. The subsequent HD session should initiate immediately following the 30 minute blood draw.

In Period 2, the HD period will be approximately 4 hours for all subjects. Blood samples collected during HD will be collected from both the pre-dialyzer and post-dialyzer blood lines.

The blood flow, dialysate flow, and the make and model of the dialyzer will be recorded.

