### 11.1.3 Hemodialysis: Plasma and Dialysate

For subjects in Panel E, the following pharmacokinetic parameters for plasma MK-3866 will be calculated as appropriate:

Ca: Concentration in plasma entering the dialyzer line (arterial or pre-dialyzer line)

Cv: Concentration in plasma exiting the dialyzer (venous or post-dialyzer line)

AUCD: Plasma AUC values determined from Ca versus time profile during the dialysis period (0.5-4.5 hours) using 'linear up, log down' calculation method option in WinNonlin

AUC(1-4.5)Ca: Plasma AUC values determined from Ca versus time profile during the dialysis period from 1 hour to 4.5 hours using 'linear up, log down' calculation method option in WinNonlin

AUC(1-4.5)Cv: Plasma AUC values determined from Cv versus time profile during the dialysis period from 1 hour to 4.5 hours using 'linear up, log down' calculation method option in WinNonlin

CLD,plasma: Dialysis clearance based on plasma, calculated as  $Q \times R \times (AUC[1-4.5]Ca - AUC[1-4.5]Cv) / AUC(1-4.5)Ca$ , where Q is the flow rate of blood through the dialyzer, and R is the ratio of blood drug concentration to plasma drug concentration

For subjects in Panel E, the following pharmacokinetic parameters for dialysate MK-3866 will be calculated as appropriate:

CD:	Concentration in dialysate samples
AD:	Amount of drug recovered from each dialysate collection, calculated as: CD x dialysate volume
rr:	Rate of drug removal, calculated as: (CD x dialysate flow rate)
AD,total:	Cumulative amount of drug recovered from the dialysate will be obtained by integrating the rr versus time profile over the dialysis session duration, using actual times relative to the start time of dialysis
CLD,dialysate:	HD clearance based on dialysate, calculated as: AD,total/AUCD

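### CLD,plasma omits ultrafiltration and so reads low in every subject who has fluid removed; ultrafiltration is not a listed item to record, and the dialysate flow in rr is undefined

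*Combined protocol and SAP*

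**What the plan says.** Section 11.1.3 gives two routes to dialysis clearance.

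- **Plasma.** CLD,plasma = Q x R x (AUC(1-4.5)Ca - AUC(1-4.5)Cv)/AUC(1-4.5)Ca, "where Q is the flow rate of blood through the dialyzer, and R is the ratio of blood drug concentration to plasma drug concentration". The same Q multiplies the arterial and the venous term.
- **Dialysate.** rr is "Rate of drug removal, calculated as: (CD x dialysate flow rate". AD,total comes from "integrating the rr versus time profile over the dialysis session duration, using actual times relative to the start time of dialysis", and CLD,dialysate is "HD clearance based on dialysate, calculated as: AD,total/AUCD". Both inherit whichever flow enters rr. The amount per collection, AD, is defined separately: "Amount of drug recovered from each dialysate collection, calculated as: CD x dialysate volume".

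Section 10.1.5 lists what is kept from the session: "The blood flow, dialysate flow, and the make and model of the dialyzer will be recorded". Ultrafiltration is not on that list and appears nowhere else in the supplied text. The Period 2 flow chart in section 6.2 shows weight at check-in and follow-up, not before and after dialysis. Dialysate is collected "for 1 minute every half hour during HD". Section 10.2.3 leaves the collection instructions to a separate document.

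**The concern.** Period 2 uses the subject's normally scheduled session, and fluid is ordinarily removed in such a session. The documents do not say so; it is an assumption. When fluid is removed, less plasma leaves the dialyzer than enters it, and the loss of water raises Cv. A formula with equal flow in and out then credits the outlet with drug that has crossed into the dialysate, and clearance comes out too low.

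Section 8.1.2 names CLD,plasma among the measures of how much MK-3866 dialysis removes, and section 7.2.1 wants the study to inform dosing recommendations around dialysis. The error runs in one direction and varies with each subject's fluid removal, so averaging over 8 subjects does not cancel it. If UF is not captured at the session, it may not be recoverable later.

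**Working it through.** The plan states no figure for dialysis removal, so there is nothing to reproduce first.

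**Inputs.** From the documents: the formulas in 11.1.3, and "In Period 2, the HD period will be approximately 4 hours for all subjects", that is 240 min. Assumed, because the documents give none: UF of 1 to 4 L per session, or 1000/240 = 4.2 to 4000/240 = 16.7 mL/min, with 10 mL/min as a middle value; Q x R of 200-300 mL/min; dialysate flow of 300-800 mL/min; extraction E = 1 - AUCv/AUCa of 0.3, 0.5 or 0.7. UF is taken as constant over the session.

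**Plasma side.** With Q as inlet flow:

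- removal rate = Q x R x Ca - (Q x R - UF) x Cv = Q x R x (Ca - Cv) + UF x Cv;
- integrating and dividing by AUCa, clearance = Q x R x E + UF x (1 - E);
- the plan keeps only the first term, so its relative shortfall is UF(1 - E)/[Q x R x E + UF(1 - E)].

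The omitted term is positive whenever UF and Cv are both positive. Reading Q as outlet flow does not help: removal is then (Q x R + UF) x Ca - Q x R x Cv, and the omitted term is UF x Ca, which is larger.

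A check that carries red cells explicitly used Q 300 mL/min, haematocrit 0.33, cell-to-plasma ratio 0.4, UF 12.5 mL/min, Ca 1 and Cv 0.5 (all assumed). Removal by mass balance is 126.55 and by the plan's formula 120.30. The difference, 6.25, equals UF x Cv = 12.5 x 0.5.

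Shortfall of CLD,plasma at UF 10 mL/min:

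| E | Q x R = 200 | Q x R = 300 |
|---|---|---|
| 0.3 | 7/(60 + 7) = 10.4% | 7/(90 + 7) = 7.2% |
| 0.5 | 5/(100 + 5) = 4.8% | 5/(150 + 5) = 3.2% |
| 0.7 | 3/(140 + 3) = 2.1% | 3/(210 + 3) = 1.4% |

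The largest value within these ranges is at UF 16.7, Q x R 200 and E 0.3: 11.7/(60 + 11.7) = 16.3%. The smallest is at UF 4.2, Q x R 300 and E 0.7: 1.25/(210 + 1.25) = 0.6%.

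**Dialysate side.** Spent dialysate leaves at inlet flow plus UF.

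- If the flow in rr is inlet (set) flow, the shortfall in rr, AD,total and CLD,dialysate is UF/(inlet flow + UF): 4.2/804.2 = 0.5% at the low end, 10/510 = 2.0% in the middle, 16.7/316.7 = 5.3% at the high end.
- If it is effluent flow, the shortfall is 0.
- If it is effluent flow and UF is added as well, rr is too high: at effluent flow 510 and UF 10, by 10/510 = 2.0%.

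**The case against.** A reader might infer that the amount recovered and CLD,dialysate are also low in every subject who has fluid removed, and that nothing collected could correct this. The documents do not support either inference. The plan does not say whether the flow in rr is inlet or effluent, and with effluent flow there is no bias. A timed 1-minute collection with a measured volume gives effluent flow directly, and AD, if computed from the volume actually collected, already contains the ultrafiltrate. Adding UF to rr without knowing which flow is used could create an error. What remains on this side is an undefined term. Listing dialysate flow beside blood flow and dialyzer model makes a machine setting the natural reading, but that is not stated. Section 10.2.2 requires urine collections to be weighed, while section 10.2.3 sets no such requirement for dialysate.

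The separate collection instructions, which were not supplied, may cover flow, volume or UF. That is possible and cannot be checked. It would not repair the CLD,plasma formula as written.

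The reach is also limited. For secondary Objective 1, section 11.2.3.3 models CL, AUC and Ceoi with and without dialysis, and none of these uses the dialysis formulas. The dialysis parameters get listings and descriptive statistics only. The two clearances cover different windows (1-4.5 h and 0.5-4.5 h), so exact agreement between them is not expected in any case.

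Finally, the sizes are assumed and usually a few percent. For scale, the plan's inflated log-AUC variance for severe impairment, 2 x 0.0196 = 0.0392, gives a standard error of sqrt(0.0392/8) = 0.07 on a log mean of 8 subjects. A 2% shift would be hard to see against that, although that variance is for AUC and not for dialysis clearance. All of this bears on priority; none of it removes the plasma-side bias.

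**Conclusion.** The plasma-side point holds. CLD,plasma as defined is biased low in every subject who has fluid removed, and UF is not on the list of items to be recorded. The direction follows from mass balance. The size rests wholly on assumed flows, UF and extraction: about 1-5% at extraction 0.5-0.7 with UF of 10 mL/min, 7-10% at extraction 0.3, and more only when high UF, low Q x R and low extraction coincide. The documents do not give the extraction of MK-3866, so the low-extraction case can be neither excluded nor presumed.

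For rr, AD,total and CLD,dialysate the finding is conditional: about 0.5-5% low under assumed flows if inlet flow is used, zero if effluent flow is used. This is a minor point of definition and data capture that leaves the primary AUC comparisons and the ESRD HD/non-HD ratios untouched.

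**What to change.** 1. Section 10.1.5: add UF rate or total UF volume, with session start and stop times, to the recorded items. If the rate changes during the session, record each rate with its time.
2. Section 11.1.3, CLD,plasma: add the term UF rate x AUC(1-4.5)Cv/AUC(1-4.5)Ca, and state that Q is inlet blood flow.
3. Section 11.1.3, rr: define the flow as effluent flow, for example from the measured volume of each 1-minute collection. Alternatively, use inlet flow plus UF rate if the recorded value is inlet flow. Choose one; combining effluent flow with an added UF term counts the ultrafiltrate twice.
4. Make the separate dialysate instructions agree, including volume measurement if effluent flow is derived from the collections.

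The cost is one case report form field read from the dialysis machine and small edits to two definitions. No extra samples or visits are needed. Measuring collection volumes, if that route is chosen, is a small added task at the site.

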## 11.2 Statistical Methods

The statistical analysis of the data obtained from this study will be the responsibility of the Data Management and Biometrics department at Celerion.

If, after the study has begun, changes are made to the statistical analysis plan stated below, then these deviations to the plan will be listed, along with an explanation as to why they occurred, in the Clinical Study Report (CSR).

Additional statistical analyses, other than those described in this section, may be performed if deemed appropriate.

### 11.2.1 Determination of Sample Size

The sample size selected for each population to evaluate the effect of RI on the pharmacokinetic of MK-3866 was not chosen to satisfy any a priori statistical requirement. This sample size (N=8 per group) has historically been shown to be sufficient for studies of this type and should provide adequate data to support the planned analyses. Nevertheless, estimates of the expected precision of the estimates, based on these sample sizes are presented below.

The precision of the estimates of ratios of geometric means obtained from this study can be assessed by calculating the half-width of the 90% confidence intervals expected for the given sample size and assumed variability. The estimated between-subject variance for log AUC0-∞ is 0.0196 log ng\*hr/mL from the FIH study (PN001). Since the between subject variability in subjects with severe RI has historically been seen to be 2-3 fold higher in many studies, the between subject variability obtained from healthy subjects was inflated by a factor of 2 for subjects with severe RI and was used for the following calculations. With 8 renally impaired subjects and 8 healthy matched subjects, the half-width of the 90%

confidence interval for the arithmetic mean  $AUC_{0-\infty}$  on the log scale will be  $0.151 \log \text{ng}^* \text{hr}/\text{mL}$ . The lower and upper 90% confidence limits for the true ratio of geometric means will be given by  $\text{OBS}/1.163$  and  $\text{OBS} \times 1.163$ , where OBS is the observed ratio of geometric means. Thus, for example, if the observed ratio of geometric means was 1.5, the 90% confidence interval would be (1.29, 1.74).

### 11.2.2 Subjects to Analyze

The decision as to which plasma samples collected will be assayed for evaluation of pharmacokinetics/pharmacodynamics will be collaboratively determined by the Departments of Quantitative Pharmacology and Pharmacometrics and Translational Pharmacology. If indicated, these samples may also be assayed and/or pooled for assay in an exploratory manner for metabolites and/or additional pharmacodynamic markers.

The following populations are defined for the analysis and reporting of data. All subjects will be reported, and their data analyzed, according to the treatment they actually received.

**All Subjects as Treated:** All subjects who received at least one dose of the investigational drug. This population will be used for assessments of safety and tolerability.

**Per-Protocol:** The set of data generated by the subset of subjects who comply with the protocol sufficiently to ensure that these data will be likely to exhibit the effects of treatment, according to the underlying scientific model. Compliance covers such considerations as exposure to treatment, availability of measurements and absence of major protocol violations. Any subjects or data values excluded from analysis will be identified, along with their reason for exclusion, in the CSR. At the end of the study, all subjects who are compliant with the study procedure as aforementioned and have available data will be included in the primary analysis dataset. This population will be used for the pharmacokinetic analyses.

### 11.2.3 Analysis Overview

#### 11.2.3.1 Interim analysis

An interim statistical analysis of the pharmacokinetic data obtained in moderate RI subjects will be performed, including a comparison with data in healthy control subjects from this study.

For this interim statistical analysis, values for the pharmacokinetic parameters  $AUC_{0-\infty}$ ,  $AUC_{0-\text{last}}$ ,  $AUC_{0-24}$ , and  $C_{\text{eoI}} (\text{C}_{\text{max}})$  of MK-3866 will be estimated and compared to concurrent healthy control subjects. A Linear Fixed Effects (LFE) Model will be used for the analysis of natural log-transformed pharmacokinetic parameters:  $AUC_{0-\infty}$ ,  $AUC_{0-\text{last}}$ ,  $AUC_{0-24}$ , and  $C_{\text{eoI}} (\text{C}_{\text{max}})$  separately. The LFE model will contain a categorical factor for population (moderate RI and healthy control subjects), and possible covariates for age, gender, and BMI, if statistically significant. A two-sided 90% confidence interval for the mean differences of  $AUC_{0-\infty}$ ,  $AUC_{0-\text{last}}$ ,  $AUC_{0-24}$ , and  $C_{\text{eoI}} (\text{C}_{\text{max}})$ , of MK-3866 will be calculated based on the above model. These confidence limits will then be exponentiated to

obtain confidence intervals for the GMR (moderate RI /healthy) for AUC0- $\infty$ , AUC0-last, AUC0-24, and Ceoi (Cmax) of MK-3866. Individual and mean concentrations versus time plots profiles will be also be provided.

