## 9 INVESTIGATIONAL PLAN

### 9.1 Overall Study Design and Plan

This is an open-label, 2-part, single dose study in renal impaired and healthy control subjects. Part 1 will include subjects with mild, moderate, and severe RI and healthy control subjects, and Part 2 will include subjects with ESRD undergoing HD. Parts 1 and 2 of the study may be conducted concurrently.

Screening of subjects will occur within 28 days prior to dosing in Part 1 or prior to the first dose in Part 2. Up to thirty-two (32), adult, male and female (non-childbearing potential only) subjects with RI, and at least 8 (up to 24) age- and BMI-matched healthy control adult male and female subjects will be enrolled.

Study parts and assignment to a renal function group will be as follows:

Panel	RI Group	N	eGFR (mL/min/1.73m  )*
Part 1			
A	Mild	8	60 ≤ eGFR < 90
B	Moderate	8	30 ≤ eGFR < 60**
C	Severe	8	< 30, not on dialysis
D	Healthy Matched Control	≥ 8	≥ 90
Part 2			
E	ESRD requiring HD	8	requiring HD

\* eGFR based on MDRD equation at screening. Baseline eGFR will be obtained by taking the mean of the eGFR obtained from screening and from historical values within a 3-month period from screening. If no historical measurement is available, a second baseline eGFR sample will be taken during the screening period (≥ 72 hours apart) and the mean of the two values will be used for group assignment; the second baseline eGFR sample may be obtained at the time of check-in.

\*\* Reasonable efforts will be made to enroll at least 2 subjects with eGFR values of 30 - 40 mL/min/1.73m^2

Subjects with mild (Panel A), moderate (Panel B), and severe (Panel C) RI and those with ESRD on HD (Panel E) shall be enrolled in parallel, and each panel shall enroll a minimum of 2 subjects of each gender.

Panel D: At least 8 and up to 24 healthy subjects (eGFR ≥ 90 mL/min/1.73 m^2), matched to the gender, mean age (± 15 years) and BMI (± 10%) of subjects in the mild, moderate, severe RI, and subjects with ESRD panels (Panels A, B, C, and E) as follows:

Enrolment of 8 healthy matched control subjects (Panel D) will commence following the completion of enrolment of Panels A and B. Each healthy control subject will be matched to

the mean age ( $\pm 15$  years) and the mean BMI ( $\pm 10\%$ ) of the subjects in Panels A and B combined. There should be a minimum of 2 subjects of each gender in each panel.

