### 9.2.1.2 Healthy Subjects

Subjects must fulfill all of the following inclusion criteria to be eligible for participation in the study, unless otherwise specified:

1. Healthy adult male or female (non-childbearing potential only) subjects, 18-75 years of age, inclusive, at screening. Age must be within  $\pm$  15 years of the mean age of subjects within the RI panel(s) to which the subject is matched.
2. Has a BMI  $\geq$ 18.0 and  $\leq$ 40.0 kg/m^2, at screening. BMI must be within  $\pm$  10 % of the mean BMI of subjects within the RI panel(s) to which the subject is matched.
3. Medically healthy with no clinically significant medical history, physical examination, vital signs, 12-lead ECGs, and clinical laboratory safety tests performed at screening.
4. Blood urea nitrogen, liver function tests (ALT, AST, alkaline phosphatase [ALP]), and serum bilirubin (total and direct) must be within the upper limit of normal for the laboratory used by the clinical site. Abnormal serum creatinine and urinalysis results must be determined to not be clinically significant by the Investigator.
5. Females must be of non-childbearing potential and are defined as:
  - Postmenopausal: defined as, without menses for at least 1 year and has a documented FSH level in the postmenopausal range at screening.
  - Surgically sterile: defined as, status post hysterectomy or oophorectomy, or tubal ligation.NOTE: These procedures must be confirmed with medical records or via pelvic exam or ultrasound scan, as applicable. In the absence of documentation, oophorectomy may be confirmed by hormone levels, particularly FSH in the postmenopausal range, but tubal ligation subjects without records should be excluded. Information must be captured appropriately within the site's source documents.
6. Male subjects with female partner(s) of child-bearing potential must agree to use a medically acceptable method of contraception during the study and for 90 days after

dosing. If their partner is pregnant, males must agree to use a condom; if their partner is of child-bearing potential, their partner must additionally be using one of the following methods: hormonal contraception, intra-uterine device, diaphragm, or cervical cap. Spermicides alone are not an acceptable method of contraception.

7. Male subjects must agree not to donate sperm from the first dosing until 90 days after dosing.
8. Have adequate venous access, as determined by the Investigator or designee, at screening.

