### 11.2.3.2 Primary Analysis

If a different group of healthy matched control subjects are needed to match the mean age and BMI for the RI and ESRD groups, then separate analyses will be performed for the populations as follows:

- Mild RI and moderate RI versus an appropriate group of healthy matched control subjects;
- Severe RI versus an appropriate group of healthy matched control subjects;
- ESRD subjects (non HD and HD) versus an appropriate group of healthy matched control subjects.

If a single set of healthy matched control subjects can be used for comparison with all RI and ESRD groups, the following analysis will be used.

Separately for each pharmacokinetic parameter, individual values of AUC0- $\infty$ , AUC0-last, AUC0-24, Ceoi (Cmax), and CL will be natural log-transformed and evaluated with a linear fixed-effects model containing a categorical effect for populations. The REPEATED statement with the GROUP=Population option will be used in SAS PROC MIXED to estimate separate variances for each population. The Kenward and Roger adjustment will be used to calculate the denominator degrees of freedom for the fixed-effect (DDFM=KR).

Ninety-five percent (95%) confidence intervals for the least squares means for each population will be constructed on the natural log scale and will reference the t-distribution. Exponentiating the least-squares means and their corresponding 95% confidence intervals will yield estimates for the population geometric means and confidence intervals about the geometric means on the original scale.

To compare subjects with RI in each of the renal categories (mild RI, moderate RI, severe RI, ESRD nonHD and ESRD HD) to matching subjects with normal renal function, a two sided 90% confidence interval for the true difference in means (RI/normal renal function) will be calculated for each PK parameters (AUC0- $\infty$ , AUC0-last, AUC0-24, Ceoi (Cmax), and CL) using the mean square error from the model and referencing a t-distribution. For each of the RI populations, these confidence limits will be exponentiated to obtain the 90% confidence interval for the true ratio of geometric means (RI/normal renal function) for each pharmacokinetic parameter.

Figures showing individual pharmacokinetic values with GMs (95% confidence intervals) by population, plotted on the natural log scale, will be provided for AUC0- $\infty$ , AUC0-last, AUC0-24, Ceoi (Cmax), and CL.

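### The interim moderate-RI comparison keeps age, gender and BMI only if significant, with no threshold or procedure, so its nominal 90% interval covers somewhat less than 90% and its model departs from the primary one

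*Combined protocol and SAP*

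**What the plan says.** Section 11.2.3.1 (Interim analysis): AUC0-∞, AUC0-last, AUC0-24 and Ceoi (Cmax) in moderate RI "will be estimated and compared to concurrent healthy control subjects". Each parameter is log-transformed and modelled separately, with a two-level population factor "and possible covariates for age, gender, and BMI, if statistically significant". The two-sided 90% interval "will be calculated based on the above model" and is then exponentiated. The section says nothing on the significance level, the order of testing, the variance structure or the degrees of freedom.

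Section 11.2.3.2 (Primary Analysis) covers the same moderate RI/normal contrast. There the log-transformed values are "evaluated with a linear fixed-effects model containing a categorical effect for populations", with no covariates. A grouped REPEATED statement "will be used in SAS PROC MIXED to estimate separate variances for each population", and Kenward-Roger degrees of freedom are specified.

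Section 9.1 matches the first 8 controls to the mean age and BMI of Panels A and B combined, not to the moderate panel alone. Section 9.2.1.2 sets the individual limits at 15 years either side ("years of the mean age of subjects within the RI panel(s) to which the subject is matched") and 10% of mean BMI.

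Section 12.2.1 has no prespecified criteria for stopping the trial early.

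**The concern.** An interval computed as if the model had been fixed, when the data chose it, is usually too short. A covariate is kept when it happens to explain residual variation in this sample. The residual variance is then understated, and the degrees of freedom do not count the search. With 16 subjects and three candidates this is not negligible.

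Two further consequences follow from the text. Selection is run separately for four parameters, so AUC and Ceoi ratios from the same subjects can be adjusted for different covariates. And because the covariate clause is absent from Section 11.2.3.2, the interim and final ratios for moderate RI can differ through the model alone.

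The missing threshold also matters for transparency. Section 11.2 requires departures from the stated plan to be listed in the study report. A threshold chosen after seeing the data would not show up as a departure, because none was stated.

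**Working it through.** **1. The plan's own precision figure.** Section 11.2.1 gives a log variance of 0.0196 (SD 0.14), doubled for severe RI, with 8 v 8 subjects.

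Half-width = t(0.95, 14) × √(0.0196/8 + 0.0392/8) = 1.761 × 0.0857 = 0.151. Then exp(0.151) = 1.163, and 1.5/1.163 = 1.29, 1.5 × 1.163 = 1.74. This reproduces the plan's figures. With equal variances of 0.0196 the half-width is 1.761 × √(2 × 0.0196/8) = 0.123.

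**2. How often an irrelevant covariate enters.** For three roughly independent tests at level α the chance is 1 − (1 − α)³: 14.3% at α = 0.05, 27.1% at 0.10, 38.6% at 0.15 and 48.8% at 0.20. The simulated rates below agree.

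**3. Coverage of the nominal 90% interval.** Setting: 8 v 8, population factor, candidates age, BMI and gender (at least 2 of each gender per group, as in Section 9.1), groups otherwise balanced, no covariate effect. The interval is the estimate ± t(0.95, residual df) × SE from the retained model, by ordinary least squares. There were 25,000 simulated trials per cell (Monte Carlo error about 0.2 points). Procedures and thresholds are assumptions.

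| Threshold | One at a time | Forward | Backward | Single drop from full model | Any covariate kept |
|---|---|---|---|---|---|
| 5% | 88.5% | 88.2% | 87.6% | 88.7% | 13–15% |
| 10% | 87.6% | 87.3% | 86.9% | 87.5% | 25–29% |
| 15% | 87.0% | 87.1% | 86.8% | 86.8% | 35–40% |
| 20% | 86.8% | 86.3% | 86.3% | 86.5% | 45–51% |

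Fixed models for comparison (50,000 trials each): population only 89.8%; all three covariates always included 90.1%. The loss in the table is 90 − 88.7 = 1.3 to 90 − 86.3 = 3.7 points; separate runs of 12,000 extend the best 5% figure to 88.9%, a loss of 1.1.

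In a run of 6,000 trials with backward selection at 5%, the mean log half-width was 0.118, against 0.121 for population only. The selected interval is slightly shorter when it should be longer.

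**4. Consistency across parameters and with the final model.** With no true effects and 4:4 gender splits, two outcomes with an assumed correlation of 0.8 down to 0.3 ended with different covariate sets in 19–27% of trials at 5% and 30–45% at 10%. When an irrelevant covariate entered at 5%, the ratio moved from its population-only value by a median factor of 1.02 to 1.05 across gender splits from 4:4 to 6:2 v 2:6 (90th percentile 1.07 to 1.11).

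**5. Is the unadjusted model enough alone?** Suppose age and BMI are each shifted by 1 SD between the groups, and age has a real effect of 0.5 residual SD per SD. Both are assumptions; the documents give no age effect. The expected unadjusted log bias is 0.5 × 1 × 0.14 = 0.07, a factor of exp(0.07) = 1.07.

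| Model | Coverage, effect 0.5 | Coverage, effect 1 | Log bias, effect 0.5 |
|---|---|---|---|
| Population only | 78% | 62% | 0.07 |
| Population + gender | 79% | 63% | 0.07 |
| Selected (5%, backward) | 78–80% | 83–85% | 0.03 |
| All three always in | 90–91% | 90% | 0.00 |

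The ranges come from separate simulation runs. Only the full fixed set holds its level here.

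**The case against.** The strongest reply is that little depends on this interval. The interim carries no decision rule, Section 12.2.1 has no stopping criteria, and Section 11.2.3.2 re-estimates the contrast without selection. At a 5% threshold about 85% of trials keep no irrelevant covariate, and the larger losses need looser thresholds that the plan does not state. All of this stands, and it limits the weight. It does not make an unstated data-driven rule a sound basis for an interval labelled 90%.

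A second reply is that selection can help. The last table bears this out: with a real age effect and an imbalance, the selected model is less biased than the unadjusted one. A reader might infer that simply deleting the covariates is always safer. The figures do not support that, because matching to Panels A and B combined, within 15 years and 10% of BMI, allows imbalance against the moderate panel.

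A reader might also infer that the two sections contradict each other on variances and degrees of freedom. They do not: Section 11.2.3.1 is silent on both, and only the covariate clause is a positive difference.

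Finally, Section 9.1 calls the controls "matched to the gender, mean age" and BMI-matched, while the only numeric gender rule is a minimum of 2 of each. A reader might infer that gender needs its own adjusted analysis of every final ratio. The documents report no gender effect on exposure. The damaging split (6:2 v 2:6) has a probability of only about 3 to 5% under the assumed shares. Gender has no better claim to separate treatment than age or BMI.

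**Conclusion.** The point holds as a minor one. The certain part is textual: a significance-based covariate rule with no threshold or procedure, applied parameter by parameter, feeding a nominal 90% interval, and absent from the primary model for the same contrast. The size is a simulation result: about 86 to 89% actual coverage with 8 v 8, no covariate effect and balanced groups. It rests on assumed thresholds of 5 to 20% and assumed procedures.

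The loss is larger under chance imbalance. With a 1 SD shift in age and BMI and still no covariate effect, coverage was about 86% at a 5% threshold and 83 to 84% at 20%.

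It would be tempting to conclude that the trial's primary renal-impairment ratios are compromised. The documents do not support that, because Section 11.2.3.2 contains no covariate selection and its intervals are untouched.

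**What to change.** In Section 11.2.3.1, remove the significance condition and fix the covariate set before interim data are seen, the same for all four parameters:

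- Main interim model: that of Section 11.2.3.2, with population only, separate variances by population and Kenward-Roger degrees of freedom. Section 11.2.3.2 also refers to the model's mean square error when describing the interval, so the interim text should say outright that the standard error uses the separate variances.
- One prespecified sensitivity analysis that always includes age, gender and BMI together, reported beside the main ratio whatever the covariates' p-values.

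The cost is a change of wording and one extra table from data already collected at screening. Recruitment and the final analysis are unchanged. The downside is precision in the sensitivity analysis. Under the ordinary least-squares calculation, residual degrees of freedom fall from 16 − 2 = 14 to 16 − 5 = 11. At SD 0.14 the mean log half-width rises from about 0.121 to about 0.140, that is, from a factor of exp(0.121) = 1.13 to exp(0.140) = 1.15.
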